1.0 Research Design

1.1 Purpose/Specific Aims

A. Objectives

This study will examine the feasibility, acceptability, and utility of neuroimaging technique to evaluate pre-exposure prophylaxis (PrEP) promotion messages for men who have sex with men (MSM) at risk of HIV in Baltimore, MD. The **specific aim** is:

Evaluate the effectiveness of PrEP promotion messages developed via a crowdsourcing open contest¹ by assessing neural bases of persuasion.

B. Hypotheses / Research Question(s)

This is an experimental study using neuroimaging technique to assess the persuasiveness of messages developed by a crowdsourcing open contest approach the study team conducted previously.

We hypothesize that, compared with participants viewing messages developed by a social marketing approach:

- H1. Participants viewing top messages developed via open contests will show higher brain activation in the Medial Prefrontal Cortex (MPFC) regions.
- H2. A greater proportion of participants viewing top messages developed via open contests will report increased willingness and behavioral intention to take PrEP.
- H3. A greater proportion of participants viewing top messages developed via open contests will report taking PrEP action and initiation during 30-day follow up.
- H4. Brain activation in the MPFC regions is significantly more correlated with PrEP action and initiation than self-reported message effectiveness.

1.2 Research Significance

With the release of pre-exposure prophylaxis (PrEP) clinical guidelines by the CDC, there has been increased effort to identify effective strategies for increasing awareness, acceptability, and uptake of PrEP as a HIV primary prevention tool, especially among men who have sex with men (MSM). Pre-testing the effectiveness of campaign materials prior to large-scale implementation is highly beneficial given the significant expenditures associated with the implementation of a large-scale campaign. Evidence in neuroscience has demonstrated that neural responses hold the potential to be significantly more reliable than self-report measures to assess message effectiveness that is highly predictive of future behavior change.² Successful persuasion has been associated with brain activity in Medial Prefrontal Cortex (MPFC), through a process of self-integration (i.e. increased brain activity for messages and cues that are successfully integrated with one's self-concept).³

This proposal will examine the feasibility, acceptability, and utility of neuroimaging technique to evaluate PrEP promotion messages for MSM at risk of HIV in the United States. Findings of this proposed study will transform the design, evaluation, and implementation of HIV

campaigns, potentially bringing new ideas for local health departments and community-based organizations in developing more impactful PrEP campaigns.

1.3 Research Design and Methods

This study is a randomized control trial (RCT). A total of 60 participants will be recruited and enrolled into this RCT where half of them will view PrEP promotion messages developed via a crowdsourcing open contact¹ and half of them will view PrEP promotion messages developed via social marketing.

A. Research Procedures

This study will be conducted as follows:

- Screening will be conducted in person after an oral consent. Once an individual is screened eligible, he will provide an informed consent and complete a baseline survey. A 2nd in-person visit will be scheduled, roughly a week after completing the baseline survey.
- During the in-person visit, participants will be randomized to one of two conditions: a) viewing top three messages developed by an open contest implemented in Baltimore, or b) viewing PrEP campaign messages that were developed with a traditional social marketing approach.
- After the randomization, a research assistant will take the participant to a private interview room. The research assistant will measure and fit the participant's head for the fNIRS headband, which is connected to a NIRSport. NIRSport is a portable fNIRS device to measure the neural response as participants view various messages on a computer screen with audio computer assistance. Similar to functional magnetic resonance imaging (fMRI), fNIRS is a non-invasive neuroimaging technique to measure key brain regions associated with influence and persuasion. Unlike fMRI, fNIRS only collects data ~3 cm into the cortex, yet the advantages of fNIRS are that it is small, portable, quiet, and does not require being still in a narrow tube. Employing harmless light sources, fNIRS is safe for studies with infants and adults as well. fNIRS involves wearing a lightweight cap from which LED lights are directed into the brain. The LED light emerges from the brain in predictable patterns and the way in which active brain tissue absorbs light allows us to reconstruct fMRI type images of the activity in the cortical surface. fNIRS have been widely used in social neuroscience research.
- Participants in each group will view multiple messages on a computer screen while brain activity is recorded.
- After completing all messages, participants will answer questions on perceived effectiveness of the messages, self-efficacy, and willingness and behavioral intention to use PrEP. Semi-structured questions on the acceptability of fNIRS will also be asked.
- All participants will complete a 30-day follow up survey by phone call or online to assess any behavioral change.

B. Data Points

- 1) Baseline: survey
- 2) In-person visit: neuroactivity and survey
- 3) 30-day follow up: online or phone survey

C. Study Duration

2 months

D. Endpoints

N/A

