1.6 Study Variables

A. Independent Variables, Interventions, or Predictor Variables

Intervention: top three messages developed by an open contest implemented in Baltimore¹.

B. Dependent Variables or Outcome Measures

Brain activity: fNIRS detects the ratio of oxygenated (O₂HB) to deoxygenated (HHB) hemoglobin based on their optical properties, with higher ratios indicating greater neural activity. Neural tissues are relatively transparent to light in the near infrared range between 700-1000 nm, and O₂HB and HHB reflect distinct wavelengths in this range. By modulating light at different wavelengths, emitting the light on the skin-exposed areas of the cranium, and detecting that light, fNIRS measures the blood oxygenation level dependent signal (BOLD) like fMRI. Because the photons reflected from neural tissue follow a reliable 'banana-shaped' path, photodetectors can be used to measure this on the scalp. By measuring the amount of absorbed light directed at the neural tissue, we can measure the amount of O₂HB and HHB present in a region of the brain at a given time and draw inferences about the level of neural activity.

PrEP-related beliefs, willingness, behavioral intention, and behavior:

All questions will be asked to participants at baseline (only to individuals aware of PrEP), at the in-person visit after reviewing all messages, and at the 30-day follow up, except questions on PrEP action and initiation, which will only be asked at the 30-day follow up.

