6.0 Data Management Plan

6.1 Data Analysis

Our primary aim in this study is to assess the effectiveness of PrEP promotion messages developed via open contest by assessing brain activation in the regions associated with persuasion (i.e., Medial Prefrontal Cortex (MPFC)), and any changes in participants' PrEP willingness, behavioral intention, initiation, and action in 30-day follow up. We will first assess whether the randomization has worked by comparing baseline demographic and confounding variables of participants in each arm using Fisher's exact test for dichotomous variables, analysis of variance (ANOVA) tests for nominal variables and normally distributed continuous variables, and Wilcoxon signed-rank tests for non-normally distributed continuous variables, with statistical significance determined at alpha=0.05. Any variable for which randomization did not result in equal proportions in each arm will be incorporated into the multivariate models as a potential confounding variable.

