Next, we will conduct primary inferential analyses to compare a) the level of neural activity in MPFC, b) increase in willingness and behavioral intention to take PrEP between baseline and 30-day follow up (yes/no), and c) PrEP action and initiation at 30-day follow up (yes/no) among participants in the three conditions. fNIRS detects the ratio of oxygenated (O₂HB) to deoxygenated (HHB) hemoglobin based on their optical properties, with higher ratios indicating greater neural activity. By modulating light at different wavelengths, emitting the light on the skin-exposed areas of the cranium, and detecting that light, fNIRS measures the blood oxygenation level dependent signal (BOLD) similar to fMRI. Because the photons reflected from neural tissue follow a reliable 'banana-shaped' path, photodetectors can be used to measure this on the scalp. By measuring the amount of absorbed light directed at the neural tissue, we can measure the amount of O₂HB and HHB present in a region of the brain at a given time and draw inferences about the level of neural activity. The level of brain activation for the top message condition compared to references will be evaluated using pairwise comparison. For the binary outcome measures, increase in willingness and behavioral intention to take PrEP and PrEP action and initiation, we will first compare proportions by conditions separately for each measurement period using standard bivariate analytic techniques such as Spearman rank-order correlations, odds ratios, and Fisher's exact test. Then we will employ generalized linear mixed

models (GLMM) to evaluate the effectiveness of top messages developed via open contest. GLMM permits us to measure the fixed effect of the top messages developed via open contest on neural activity, willingness and behavioral intention to take PrEP, and PrEP action and initiation, while allowing a random effect that accounts for within-person correlation. Given the binary nature of two primary outcomes, we will specify a logit link function for our GLMM models. Comparisons of characteristics of participants who are lost to follow-up to those who are evaluated will be conducted to assess for systematic patterns that could influence results.

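### No randomisation method or fixed baseline covariate is specified, although PrEP awareness and intention are on file a week before allocation; the test-then-adjust rule in 6.1 would miss most sizeable imbalances.

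*Combined protocol and SAP*

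**What the plan says.** - **Allocation (1.3).** The plan states that "A total of 60 participants will be recruited and enrolled into this RCT where half of them will view PrEP promotion messages" from the open contest, with the other half viewing social-marketing messages. On how men are allocated it says only that "During the in-person visit, participants will be randomized to one of two conditions". Sequence generation, blocking, stratification, minimisation and concealment are not described anywhere.
- **Timing (1.3).** Eligible men complete the baseline survey first: "A 2nd in-person visit will be scheduled, roughly a week after completing the baseline survey". Their baseline answers are therefore held before allocation.
- **Baseline items (1.6 and 1.9).** For beliefs, willingness and intention, "All questions will be asked to participants at baseline (only to individuals aware of PrEP"). Awareness must therefore be established at baseline for every man, while intention is recorded only for aware men.
- **H2 outcome (6.1).** It is defined as "increase in willingness and behavioral intention to take PrEP between baseline and 30-day follow up (yes/no").
- **Handling of imbalance (6.1).** "We will first assess whether the randomization has worked by comparing baseline demographic and confounding variables", at alpha 0.05. The plan continues: "Any variable for which randomization did not result in equal proportions in each arm will be incorporated into the multivariate models". No covariate is named in advance.
- **Purpose (1.5).** The trial seeks preliminary evidence and effect-size estimates for designing a fully powered study. No power, rates or effect size are given.

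**The concern.** The trial holds two pieces of information on each man that plausibly bear on the outcomes, and it commits to using neither, at allocation or in the models.

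Awareness matters for a reason that needs no assumption about prognosis. A man unaware of PrEP at baseline has no starting value for willingness or intention, so an uneven split of awareness gives the arms different numbers of men with a usable H2 baseline. Intention to begin PrEP is an obvious candidate predictor of acting on PrEP within 30 days (H3), though the documents give no figure for its strength.

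The protection in 6.1 depends on a significance test with 30 men per arm. If that test seldom detects gaps large enough to move the estimates, those gaps stay in the unadjusted results. They then pass into the effect sizes used to plan the next trial.

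**Working it through.** **Inputs.** From 1.3: 60 men, half per arm, so 60/2 = 30. From 6.1: Fisher's exact test for dichotomous baseline variables at 0.05 (sidedness not stated; two-sided assumed). The plan gives no power calculation to reproduce. It also gives no awareness or intention rates and no prognostic strength, so these are assumed and shown as ranges.

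**Step 1: how often a sizeable gap arises.** With K of 60 men having a factor and a fixed 30:30 split, the number x in one arm is hypergeometric(60, K, 30). The gap is |x − (K − x)|/30. A gap of 20 points means a difference of at least 6 men.

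**Step 2: how often the test sees it.** For each x, Fisher's test is applied to x/30 against (K − x)/30.

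| Assumed prevalence | P(gap ≥ 20 points) | Smallest gap flagged | P(gap ≥ 20 points, not flagged) | Share missed |
|---|---|---|---|---|
| 50% | 0.196 | 20 v 10 (33 points) | 0.177 | 0.177/0.196 = 90% |
| 70% | 0.158 | 25 v 17 (27 points) | 0.111 | 0.111/0.158 = 70% |
| 80% | 0.104 | 28 v 20 (27 points) | 0.083 | 0.083/0.104 = 80% |
| 90% | 0.024 | 30 v 24 (20 points) | 0 | 0% |

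The problem is confined to factors that are not close to universal. At 90% prevalence such gaps are rare and all are flagged. By symmetry, 30% prevalence gives the 70% row.

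**Step 3: what an unadjusted gap does.** The shift in the arm difference is the gap times the effect of the factor on the outcome. For a 20-point gap and an assumed effect of 20, 35 or 50 points, the shift is 0.20 × 0.20 = 4, 0.20 × 0.35 = 7 or 0.20 × 0.50 = 10 points. Its direction is random, so over repeated trials it averages to zero.

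**Step 4: what prespecified adjustment is worth.** Assume 30% of men plan to begin PrEP and that the others act at a rate of 20%. With an effect of D, the overall rate is p = 0.20 + 0.30·D, the variance explained is R² = 0.30 × 0.70 × D²/[p(1 − p)], and the equivalent extra sample is 60 × [1/(1 − R²) − 1].

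| D | p | R² | Extra participants |
|---|---|---|---|
| 0.20 | 0.260 | 0.21 × 0.0400/0.1924 = 0.044 | 2.7 |
| 0.35 | 0.305 | 0.21 × 0.1225/0.2120 = 0.121 | 8.3 |
| 0.50 | 0.350 | 0.21 × 0.2500/0.2275 = 0.231 | 18.0 |

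This is linear-model arithmetic. Section 6.1 specifies a logit link for the binary outcomes, so the figures indicate scale only.

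**Step 5: what stratified allocation adds once the term is in the model.** With n_s men in stratum s and x_s of them in one arm, the adjusted variance relative to perfect balance is [1/Σ x_s(n_s − x_s)/n_s]/(2/30). Simulating unstratified 30:30 allocation gives a mean excess of 1.8% for awareness alone (95th percentile 5% to 8%) and 3.6% for three strata (95th percentile about 10%). On average that is about 0.018 × 60 = 1 to 0.036 × 60 = 2 participants.

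**The case against.** Several points on the other side stand.

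- **Silence is not a design.** A reader might infer that allocation is unrestricted and will therefore miss the stated half-and-half split. Simple randomisation would give exactly 30:30 in only 10% of trials and a split worse than 35:25 in 15.5%. The documents do not say simple randomisation is used, and the stated split fits a restricted method at least as well. What can be said is that the method is not specified.
- **The plan does address imbalance.** It would be wrong to say imbalance is simply left to chance, because 6.1 has an adjustment rule. Read literally, that rule could bring in any variable that is not exactly equal. Coming straight after a 0.05 test, it more naturally reads as a significance screen. On either reading, the covariates are chosen after seeing the data.
- **Predictive strength is not documented.** A reader might take awareness and intention to be the strongest predictors available. No section says so or gives a figure. For H1 no link with either variable is shown.
- **The gain comes from the model.** Nearly all of it comes from including the covariate, so stratifying at allocation is a refinement.
- **Large gaps are the minority case.** At prevalences of 50% to 80%, between 80% and 90% of trials would have no 20-point gap.
- **The trial is preliminary.** Section 1.5 says so, which limits the severity.

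None of this rescues the test-then-adjust rule, which fixes no covariate in advance and misses most of the gaps it is meant to find at prevalences of 50% to 80%.

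**Conclusion.** The concern holds in a limited form. The randomisation method is unspecified, no baseline variable is fixed as a covariate, and the screen in 6.1 misses about 70% to 90% of gaps of 20 points or more at assumed prevalences of 50% to 80%. The consequence is lost precision and less trustworthy effect estimates in one small trial. A reader might infer bias, but chance imbalance under randomisation does not bias the comparison on average.

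The benefit of a prespecified term, roughly 3 to 18 participants' worth, rests on assumed rates and on awareness and intention being good predictors. The effect of awareness on how many men have an H2 baseline follows from the plan's own definitions. Severity is minor to moderate.

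**What to change.** **Main change (6.1).** Replace the test-then-adjust rule with one prespecified fixed term in the H1 to H3 models. It is a three-level baseline group: not aware of PrEP; aware and not planning to begin; aware and planning to begin. State the cut-point on the graded intention item that separates the last two levels. The unaware level lets every man be classified even though intention is not asked of all. The cost is a few lines of text and two model degrees of freedom.

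**Optional addition (1.3).** State the allocation method: 1:1, in concealed, computer-released permuted blocks of varying size, stratified by the same group. This secures the half-and-half split and saves the further 2% to 4% of variance. The cost is three pre-generated lists and a look-up of two answers before the second visit. The downsides are some predictability with small blocks and possibly incomplete blocks in the smallest stratum. If stratification is not wanted, the method actually used should still be stated.

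**To settle separately.** Neither change says what an increase since baseline means for men who were not asked the willingness and intention items at baseline. The plan must define the H2 outcome for them, or state that H2 is restricted to men aware at baseline.

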4.3 Number of Subjects

A. Total Number of Subjects

We expected to screen 100 individuals. Seventy will be eligible and consent for participation. We need 60 individuals to complete the study.

B. Total Number of Subjects If Multicenter Study

N/A

C. Feasibility

[name] has a long history of working with local community partners to recruit study participants.

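### Randomisation comes before the fNIRS headband is fitted, so fitting failures are post-allocation losses to the neural analyses (H1, H4), and nothing stated keeps the fitter unaware of the arm

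*Combined protocol and SAP*

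**What the plan says.** Section 1.3 (A. Research Procedures) sets out the second visit in order. First comes allocation: "During the in-person visit, participants will be randomized to one of two conditions". Then: "After the randomization, a research assistant will take the participant to a private interview room". Next: "The research assistant will measure and fit the participant's head for the fNIRS headband, which is connected to a NIRSport". The messages are shown after that, with recording during viewing.

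Two hypotheses in section 1.1 depend on the recording. H1 is the between-arm contrast: "Participants viewing top messages developed via open contests will show higher brain activation in the Medial Prefrontal Cortex (MPFC) regions". H4 is the association: "Brain activation in the MPFC regions is significantly more correlated with PrEP action and initiation than self-reported message effectiveness". H2 and H3 rest on survey answers.

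The first visit is a survey only (sections 1.3 and 1.9). None of the seven inclusion criteria in section 4.1 concerns fNIRS, and no exclusion criteria are listed. Section 1.4 mentions an equipment manual, whose content is not included. Section 6.1 plans to compare the characteristics of participants lost to follow-up with those evaluated. It gives no signal-quality threshold, no rule for unusable recordings and no analysis population. The available text is silent on who holds the allocation and whether staff are blinded to it.

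**The concern.** Fit, tolerance and signal are first tested on people who already have an arm. Section 4.7 itself foresees discomfort from the headband, so some refusals are to be expected. Each failure at this stage removes a randomised participant from H1, the first comparison listed in section 6.1, and from H4.

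Two consequences are possible. The first is loss of precision in a trial of about 30 per arm. The second arises only if the fitter knows the arm: persistence in refitting, or willingness to accept a marginal signal, could then differ between arms and make the MPFC contrast selective. No described step needs the arm before the first message appears, so the present order carries this exposure without any stated gain.

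**Working it through.** **Order of steps.** Section 1.3 gives: randomise, go to the room, measure and fit, view messages with recording. Sections 1.3, 1.9 and 4.1 contain no earlier check of fit or signal. Fitting failures therefore fall after allocation.

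**Which hypotheses are affected.** H1 and H4 need a recording. H2 and H3 need message viewing and surveys, so a participant with a failed fit could still contribute to them, although the plan does not say so.

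**The plan's own figures.** Section 1.5 has no power calculation to reproduce. Section 1.3 says "A total of 60 participants will be recruited and enrolled into this RCT", half per arm, which is 30 v 30. Section 4.3 says "Seventy will be eligible and consent for participation" and requires 60 to complete. The implied allowance is (70 − 60)/70 = 14.3%, with no cause or stage given. It may have to cover missed visits and 30-day losses as well as fNIRS failures.

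**Illustration.** Assumptions: two-sided alpha 0.05 (the plan states 0.05 only for the baseline comparisons), 80% power, two-sample t test, equal failure in both arms, and failure rates f of 5%, 10% and 20%, since none is given. Usable recordings per arm are n = 30(1 − f), rounded down. The detectable standardised difference is approximately (1.960 + 0.842) × √(2/n); the table gives the slightly larger values from the noncentral t distribution. For n = 30 the approximation gives 2.802 × √(2/30) = 0.723, against 0.736 exactly.

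| Assumed f | n per arm | Detectable d | Power at d = 0.736 |
|---|---|---|---|
| 0% | 30 | 0.736 | 80% |
| 5% | 28 | 0.762 | 77% |
| 10% | 27 | 0.777 | 76% |
| 20% | 24 | 0.826 | 70% |

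**Chance imbalance.** With failures in each arm distributed as Binomial(30, f), the probability that the arms differ by 3 or more failures is 13% at 5%, 27% at 10% and 42% at 20%. This matters little for precision: 54 recordings split 25.5 v 28.5 give d = 0.778, against 0.777 for 27 v 27.

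**Numbers needed for 60 usable recordings.** 60/(1 − f) gives 60/0.95 = 63.2, so 64; 60/0.90 = 66.7, so 67; and 60/0.80 = 75. The 70 consenting would suffice at 10% only if no more than 3 are lost for other reasons, and would not suffice at 20%.

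**The case against.** The strongest reply is that the bias is inferred. Section 1.3 says that the assistant measures and fits. It does not say that he or she knows the arm, judges signal acceptability or excludes anyone, and the manual in section 1.4 may contain checks. Fitting failures happen before any message is seen, so with an unaware fitter they should be unrelated to arm. This stands. A reader might infer that the MPFC contrast will be biased, but the documents do not support that. They support only that nothing stated prevents it.

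A second reply is that reordering does not remove all losses. This also stands: signal lost while messages are viewed, or recordings rejected later, are post-randomisation losses under any order.

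A third is that randomising only people with acceptable signal has a cost: it would exclude from H2 and H3 participants who could still view the messages and answer the surveys. That is a sound argument against making signal a condition of randomisation. It is not an argument against checking signal first.

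Finally, the study claims no power. Section 1.5 describes preliminary evidence and effect-size estimation, and the shift in detectable d at 10% failure is small. This limits the weight of the precision argument. It does not answer the question of selection if the fitter knows the arm, which would carry into the effect-size estimates that the study exists to provide.

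**Conclusion.** The point holds as an avoidable weakness in design, not as an error or contradiction. Failures and refusals at fitting occur after allocation and reduce the randomised set for H1 and H4, and no stated safeguard keeps the fitter unaware of the arm.

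The size is unknown. Under assumed failure of 10% or 20%, detectable d moves from 0.74 to 0.78 or 0.83. Those figures treat every failure as one that an early check would catch, so they are an upper limit on what reordering addresses at a given rate. Precision is recovered only if failed participants are replaced, because someone who cannot be fitted yields no MPFC data in either order. Bias requires a fitter who knows the arm, or exclusions decided with the arm known. H2 and H3 need not be affected.

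**What to change.** Reorder section 1.3 as follows:

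1. Measure and fit the headband, check the signal against a prespecified criterion, and record the status.
2. Generate and reveal the allocation only then, immediately before the first message.
3. Randomise everyone willing to view the messages, including those with failed fitting, so that they remain in H2 and H3.
4. Define the H1/H4 set by the fit status recorded before randomisation. Either stratify allocation by that status, or replace failures from the 70 consenting, to keep the arms balanced for the neural analyses.
5. For signal lost during viewing, add to section 6.1 a quality rule applied blind to arm, and report the losses by arm.
6. Report the fitting-failure count as a feasibility result, in line with the objective in section 1.1.

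The cost is small: no extra visit or procedure, but allocation must be run at the point of stimulus presentation. Replacement raises the number randomised above 60 and depends on how many of the 70 remain available. H1 and H4 apply only to people with a recordable signal, as they would under any order.
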